### ***Real calculation***

1.  $\alpha = 0.05$
2.  $1 - \beta = 0.8$
3.  $r = 1$
4.  $\mu_1 = 17$
5.  $\mu_2 = 15$
6.  $SD_1 = 3.5$
7.  $SD_2 = 3.5$
8.  $d = 0.18$  (18%)

### ***Number of study participants***

- Group 1: 46

- Group 2: 46
- Total: 92

After considering the dropout rate, the total required number of participants is 102.

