## **3. Study design**

[figure not shown]
This randomized, double-blind, placebo-controlled, parallel-group trial aims to enroll 120 participants. Individuals with T2D who have been on pharmacological treatment for at least 12 weeks, without any dose adjustments prior to enrollment, will be eligible for screening. The screening period will last up to two weeks before randomization. To qualify for randomization, participants must meet an 80% compliance rate, based on pill count, and the investigator's discretion during the run-in phase. After randomization, participants will be blinded to their glycated hemoglobin (HbA1c) and fasting plasma glucose (FPG) results. To maintain blinding, urinary glucose excretion (UGE) results will also be masked from participants. Urine glucose, albumin, calcium, and creatinine will be measured separately during on-site visits.

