## 7. Treatment

### 7.1. Intervention and control

After randomization, patients will undergo a 24-week double-blind treatment period. A total of 102 patients aged 20 years or older will be randomly assigned in a 1:1 ratio to one of the following two groups:

- Ertugliflozin 5 mg once daily
- Placebo (identical in appearance to ertugliflozin) once daily

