## 8. Sample size calculation

The primary endpoint of this study is the change in LVGLS from baseline to week 24. The hypothesis is that the ertugliflozin group will demonstrate superiority over the placebo group.

- Null hypothesis ( $H_0$ ):  $P_1 = P_2 \geq \delta$
- Alternative hypothesis ( $H_1$ ):  $P_1 - P_2 < \delta$

The following equation will be used for sample size estimation:

When  $r = 1$ ,

1. Type I error ( $\alpha$ ) = 5% (two-sided, default)
2. Power = 1 – Type II error ( $\beta$ ) = 80% (default)
3. Allocation ( $r$ ) = 1 (default)
4. Mean in the ertugliflozin group ( $\mu_1$ )
5. Mean in the placebo group ( $\mu_2$ )

6. Standard deviation (SD) in the ertugliflozin group ( $SD_1$ )
7. SD in the placebo group ( $SD_2$ )
8. Dropout rate ( $d$ ) = 10% (default)

Since no prior interventional studies have evaluated the effect of ertugliflozin on GLS, we referenced studies measuring LV volume. An increase in LV volume has been used as a marker for assessing the impact of drug therapy on heart failure survival [13]. It has been suggested that a 10 mL change in LV volume is clinically significant [14]. This change corresponds to a 15% change in EF in individuals with pre-HF, whose EF typically ranges from 30% to 50%. In heart failure populations, the SD for the mean difference in LV volume has been reported to be 7.5 [15]. For comparison, the EMPA-REG OUTCOME trial showed that empagliflozin reduced heart failure hospitalization by 35% [16], and the CANVAS program found that canagliflozin reduced heart failure hospitalization by 33% [17]. Based on these results, we assumed a 15% baseline GLS in both groups and a 13.2% decrease in GLS in the ertugliflozin group after treatment, with no change in the placebo group. We assumed a standard deviation of 3.5 for both groups, adopting a conservative approach. Considering an 18% dropout rate, the minimum required sample size is 100 participants (60 per group with a 1:1 randomization). Additionally, a recent study demonstrated that improvements in glycemic control (HbA1c reduction from  $10.3 \pm 2.4\%$  to  $8.3 \pm 2.0\%$ ) over a 12-month period led to a 21% improvement in GLS and a 24% improvement in cardiac function, as estimated by septal e' [18].

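### The sample size does not follow from its own inputs, and the totals stated (120, 102, 100) conflict; randomising 102 gives about 73–74% power at the stated 18% dropout, not 80%.

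*Combined protocol and SAP*

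**What the plan says.** The sample size appears in four places in the combined protocol and SAP.

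- Section 3 (Study design): "parallel-group trial aims to enroll 120 participants".
- Section 7.1 (Intervention and control): "A total of 102 patients aged 20 years or older will be randomly assigned in a 1:1 ratio".
- Section 8, narrative: "Considering an 18% dropout rate, the minimum required sample size is 100 participants (60 per group with a 1:1 randomization".
- Section 8, under Number of study participants: 46 in each group, 92 in total, and then "After considering the dropout rate, the total required number of participants is 102".

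The inputs are also in Section 8. Type I error is "5% (two-sided, default", power is 80% and allocation is 1:1. On effect size, "we assumed a 15% baseline GLS in both groups and a 13.2% decrease in GLS in the ertugliflozin group after treatment", with no change on placebo. On variability, "We assumed a standard deviation of 3.5 for both groups, adopting a conservative approach". The list under Real calculation turns these into means of 17 and 15, an SD of 3.5 in both groups and a dropout of 18%. The general list of inputs earlier in Section 8 shows a default dropout of 10%.

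**The concern.** A sample size section should let a reader go from the inputs to the number randomised. Here neither step can be followed. The evaluable number is smaller than the inputs require, and the allowance for dropout does not use the stated rate. Both errors make the trial smaller.

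The result then conflicts with other totals in the same document. Section 7.1 is where the plan says how many will be assigned to treatment. If it is followed, the comparison on the primary endpoint, change in LVGLS at week 24, has less than its stated power under the plan's own assumptions. A null result at 102 would be read against an 80% claim that does not apply to that number. And because 102 and 120 are both in the current text, stopping at either could be called as planned.

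**Working it through.** **Inputs (Section 8).** Difference 17 − 15 = 2; SD 3.5 in each group; two-sided alpha 0.05 (z = 1.960); power 80% (z = 0.842); 1:1 allocation; dropout 18%. The narrative effect is nearly the same size: 13.2% of 15 is 1.98.

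**Step 1: evaluable number per group.** For two means,

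n = 2 × (1.960 + 0.842)² × 3.5² / 2² = 48.07, rounded up to 49.

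With the t distribution, 49 per group gives 79.96% power, so 50 are needed. The plan states 46, which could not be reproduced:

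- A one-sided alpha of 0.05 gives 38.
- A difference of 1.98 gives 49.05, rounded up to 50 (51 by t).
- To reach 46 with a two-sided test at 80% power, the SD would have to be 3.42 or the difference 2.04.

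At 46 evaluable per group, power is 78.2% (normal) or 77.4% (t).

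**Step 2: allowance for dropout.** Starting from the plan's 92:

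- At 18%: 92/0.82 = 112.2, rounded up to 113. Multiplying instead gives 92 × 1.18 = 108.6, or 109.
- At 10%: 92/0.90 = 102.2. Multiplying gives 92 × 1.10 = 101.2, or 102.

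So 102 matches the 10% default and not the 18% listed under Real calculation.

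**Step 3: the chain from the stated inputs.** 2 × 49 = 98 evaluable, and 98/0.82 = 119.5, rounded up to 120, or 60 per group. This agrees with Section 3 and with the 60 per group in the Section 8 narrative. It does not agree with the 100 in that same sentence, since 2 × 60 = 120. Starting from 50 per group, 100/0.82 = 122.0, or 122.

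**Step 4: power at each stated total** (difference 2, SD 3.5, two-sided alpha 0.05, unadjusted comparison of two means).

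| Randomised | Lost | Evaluable per group | Power, normal | Power, t |
|---|---|---|---|---|
| 102 | 18% | 41.8 | 74.3% | 73.3% |
| 102 | 10% | 45.9 | 78.2% | 77.3% |
| 102 | 0% | 51.0 | 82.3% | 81.5% |
| 100 | 18% | 41.0 | 73.5% | 72.4% |
| 120 | 18% | 49.2 | 80.9% | 80.1% |

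**Step 5: the dropout that 102 can absorb.** To leave 98 evaluable, 1 − 98/102 = 3.9%. To leave 100, 1 − 100/102 = 2.0%.

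**The case against.** The arithmetic is hard to dispute, but four points can be made about its consequence.

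*The intended number is 120, so no power is lost.* This is probably what was meant, and at 120 the stated power holds. But nothing in the document ranks the totals, and 102 is given twice: as the number required and as the number to be randomised.

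*The plan may be to enrol 120 and randomise 102 after the run-in.* Section 3 does require run-in compliance before randomisation, so enrolling more than are randomised is not in itself a contradiction. However, no run-in loss is stated, Section 8 ties 60 per group to the 1:1 randomisation, and the 102 is said already to include dropout. On this reading 102 randomised would still fall short.

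*The 73–74% is conditional.* It is: it assumes that 102 are randomised, 18% are lost and the comparison is unadjusted with SD 3.5. At 10% loss the shortfall is only 2–3 points, and the error of 46 for 49 alone costs about the same. Most of the loss comes from the dropout step.

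*A baseline-adjusted analysis could recover the power.* With 41.8 per group, 80% power needs an effective SD of about 3.26 or less. The documents give no analysis model, no SD of change and no correlation between visits, so this can only be illustrated by assumption. If 3.5 is the SD at a single visit, adjustment for baseline with a correlation of about 0.36 or more would suffice. Under the same reading, comparing raw changes with a correlation of 0.3 gives an SD of 4.14 and power of about 60%. The point therefore cuts both ways and cannot support the 80% as stated.

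**Conclusion.** The concern holds. On the plan's own inputs, 46 per group should be 49 (50 by t), and 92 inflated for the stated 18% dropout is 113, not 102. Of the totals in the document, only 120 is consistent with the inputs; the exact requirement is 120 by the normal approximation and 122 by t.

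If the 102 in Section 7.1 is what is randomised and 18% drop out, the type II error is about 26–27% instead of 20%. The power figures describe the planning assumptions and not a particular final analysis, since none is specified. If 120 are randomised, the power claim is sound and what remains is the conflict between sections. It must be corrected either way, because it concerns the powering of the primary endpoint and the number at which recruitment stops.

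**What to change.** Decide which total was planned, state it once, and say that it is the number randomised.

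- **If 120:** in Section 8, replace 46, 92 and 102 with 49 per group, 98 evaluable and 120 randomised (60 per group), naming the normal approximation. Correct the 100 in the Section 8 narrative and the 102 in Section 7.1 to 120, in line with Section 3. If the t distribution is preferred, the chain is 50, 100 and 122, and Section 3 changes too.
- **If 102:** keep it in Section 7.1, align Section 3 and the Section 8 narrative with it, state power as about 73–74% at 18% dropout, and remove the 80% claim for that number.

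In both cases, remove the 10% default from the list of inputs so that one dropout rate remains.

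The cost is a text correction. For 120 there is no change to the aim already in Section 3, although it is 18 more participants than Section 7.1 provides for. For 102 the cost is a less favourable power statement.
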